9.2.2 CSF for cytology, total protein, glucose and cell count

CSF for cytology, total protein, glucose and cell count should be assessed during screening and at week 4, 8, and 26. If positive, it must be repeated within 4 weeks of the positive sampling.

9.2.3 Blood and CSF for culture

Blood and CSF will be sampled and held for potential culture after treatment doses in both cycle 1 and the conditional cycle 2. Samples will be cultured only if body temperature is elevated (defined as $\geq 38^{\circ}\text{C}$ [$\approx 100.4^{\circ}\text{F}$]) after dosing and clinical infection is suspected.

9.2.4 Demographics

The following demographic information will be recorded in the eCRF during screening:

1. Age or date of birth if allowed by local legislation
2. Gender
3. Ethnic origin
4. Race
5. Other baseline characteristics, if applicable

9.2.5 Height and body weight

Height (without shoes and rounded to the nearest centimeter) must be measured at screening and recorded in the eCRF. Body weight (without overcoat and shoes and rounded to kilogram with one decimal) will be measured and recorded in the eCRF.

9.2.6 Medical and surgical history

Medical and surgical history if any relevant medical and/or surgical event(s) previously have been experienced by the patient. Information on the patient's medical history and general health will be collected during screening and comprises of, but is not limited to:

- General medical history
- Metastases location and characterization (unifocal parenchymal, multifocal parenchymal, leptomeningeal, parenchymal and leptomeningeal)
- Tumor characteristics that allow calculation of risk classification, e.g. V-Myc Myelocytomatosis Viral Related Oncogene (MYCN) status, DNA diploidy, disease stage and LDH at the time of diagnosis, and pathology classifications.
- Any prior treatment for neuroblastoma, e.g. frontline therapy and salvage regimens, responses to prior therapy, duration of responses, sites of relapse etc.

A concomitant illness is any illness, other than the disease being investigated, which is present at trial start or found as a result of the screening procedure.

The information collected for medical history and concomitant illnesses includes:

- Diagnosis
- Date of onset
- Date of resolution
- Date of relapse, including date of CNS relapse

Any clinically significant worsening of a concomitant illness must be reported as an AE (see section 10).

9.2.7 Concomitant medication

A concomitant medication is any medication other than the IMP. All concomitant medications must be recorded in the eCRF with the following information:

- Start date
- Stop date of administration or ongoing at trial termination
- Indication/ reason for use
- Dose
- Frequency
- Outcome (for anti-cancer treatments)

Any changes to concomitant medication during the trial will be recorded in the eCRF. All doses of allowed pain relief medication should be recorded as concomitant medication in the eCRF.

9.2.8 Physical examination

Physical examination should be performed as clinically indicated from screening to the EOT and includes assessment of general appearance, mental status and various organ systems (skin, head, eyes, ears, nose, mouth, throat, neck, thyroid, lymph nodes, respiratory, cardiovascular, gastrointestinal, extremities, musculoskeletal, and neurologic systems).

9.2.9 Vital signs

Pulse oximetry and measurements of heart rate, respiratory rate, temperature, and blood pressure before and 30 minutes after ^{131}I -omburtamab infusion. Temperature must be measured by using the same method (e.g., an ear thermometer).

9.2.10 Neurotoxicity

Neurotoxicity will be assessed by the National Cancer Institute clinical neurotoxicity criteria during screening and weeks 1, 4, 5, 8, 26. All neurologic abnormalities present prior to ^{131}I -omburtamab infusions will be recorded as medical history. Any neurologic changes during the trial period which meet the criteria for Grade 3 or 4 neurotoxicity will be assessed by the trial physicians as being unrelated, possibly or probably caused by the infusion. In the absence of clear evidence progressive disease (PD), it may be assumed that new signs and symptoms are

treatment related. Any patient that develops Grade 4 neurotoxicity after the IMP infusion is to be discontinued from treatment.

Neurotoxicity also will be assessed clinically and radiographically. Assessment of cranial nerves, gross motor function and sensory function will be performed. Assessment and grading of radiographically cortical atrophy, cerebral ventricular size, white matter changes or other abnormalities will be made by a neuro-radiologist. Altered CSF flow will be interpreted by the trial nuclear medicine physicians.

Clinical neurotoxicity evaluation is to be conducted at screening and weeks 1, 4, 5, 8 and 26, as indicated in the flowchart. The radiographic assessment of neurotoxicity and disease progression (by MRI) is to be conducted at screening, weeks 4 and 8 and week 26 only.

Lansky (Karnovsky for children \geq 16 years) performance score will be analyzed to evaluate gross neurologic function and a measure of a patient's long-term function.

9.2.11 Non-childbearing potential

Non-childbearing potential in women will be confirmed by one of the following:

- Women/girls who have not reached menarche or
- Women/girls who have not had menses within the past 12 months and who do have a follicle-stimulating hormone level ≥ 40 IU/L or
- Women/girls who have not had menses within the past 24 consecutive months if a follicle-stimulating hormone measurement is not available
- Women/girls who have undergone surgical sterilization (e.g., hysterectomy, or bilateral oophorectomy, or bilateral salpingectomy).

9.2.12 Unscheduled visits

If any assessments need re-evaluation, an additional response assessment is needed, or follow up on an (S)AE is required, the patient can be called for an unscheduled visit at the discretion of the Investigator. Data obtained during unscheduled visits pertaining to the clinical trial will be collected as unscheduled visits in the eCRF.

10 ADVERSE EVENTS

10.1 Definitions

10.1.1 Definition of adverse events

An AE is any untoward medical occurrence in a patient administered a pharmaceutical product which does not necessarily have a causal relationship with the treatment.

An AE can therefore be any unfavorable and unintended sign (including an abnormal laboratory finding), symptom or disease temporally associated with the use of a product, whether or not considered related to the product.

An AE includes:

- A clinically significant worsening of a concomitant illness.
- A clinical laboratory adverse event (CLAE): a clinical laboratory abnormality which is clinically significant, i.e. an abnormality that suggests a disease and/or organ toxicity and is of a severity that requires active management. Active management includes active treatment or further investigations, for example change of medicine dose or more frequent follow-up due to the abnormality.

Throughout the clinical trial a DMC will monitor the patients' safety according to the DMC charter (section 6.2).

10.2 Definition of Serious Adverse Events

Each AE is to be classified by the Investigator as either serious or non-serious. This classification of the seriousness of the event determines the reporting procedures to be followed. An AE that meets one or more of the following criteria/outcomes is classified as serious:

- Requires inpatient hospitalization or prolongation of existing hospitalization.
- Results in persistent or significant disability/incapacity
- Is a congenital anomaly/birth defect
- Medical important medical
- Results in death
- Is life threatening

The term "life-threatening" in the definition of "serious" refers to an event in which the patient, in view of either the investigator or sponsor, was at risk of death at the time of the event; it does not refer to an event, which hypothetically might have caused death if it were more severe. Death alone is not considered an AE; it is an outcome of an AE. Reports of death should be accompanied by the corresponding AE term for the event that led to the outcome of death. However, sudden death or death due to unexplainable cause(s) should be reported as an SAE, while follow-up is pursued to determine the cause.

Hospitalization is defined as admission to a hospital/inpatient (irrespective of the duration of physical stay) or is not admitted to a hospital/not an inpatient but stays at the hospital for treatment or observation for more than 24 hours. Exceptions are hospitalizations for

administrative, surgical procedures planned before trial inclusion, trial-related and social purposes do not constitute AEs.

Elective surgery or other scheduled hospitalization periods that were planned before the patient was included in this trial are not to be considered serious. However, the event must be reported on the AE page in the eCRF and commented upon.

Medical and scientific judgment must be exercised in deciding whether an AE is believed to be “medically important”. Medical important events may not be immediately life-threatening or result in death or hospitalization but may jeopardize the patient or may require intervention to prevent one of the other outcomes listed in the definition above.

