10.6.1 Procedures

Diagnostic and therapeutic non-invasive and invasive procedures, such as surgery, should not be reported as AEs. A medical condition for which an unscheduled procedure was performed, should however be reported if it meets the definition of an AE. For example, an acute appendicitis should be reported as the AE and not the appendectomy. Additionally, any procedures pre-planned before entering the trial (e.g. for pre-existing conditions) can be excluded.

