12.4 Safety Analysis

The safety analysis set will be used for all safety analyses. Adverse event data will be listed individually, and the incidence of adverse events will be summarized by system organ class (SOC) and preferred terms for each treatment group. AEs will be coded using the Medical Dictionary for Regulatory Activities (MedDRA) version 19.0 or later. AEs will be regarded as treatment-emergent adverse events (TEAEs) if they occur after first administration of ^{131}I -omburtamab. Related AEs are defined as adverse drug reactions (ADRs).

Listings will be made of all AEs, including non-TEAEs. All TEAEs, ADRs, SAEs and serious adverse reactions (SARs) will be summarized. The summaries will include number of events, number of patients, and percentage of patients reporting these events and will be tabulated by SOC and preferred term (PT). TEAEs will also be summarized by severity and by relationship to IMP. When calculating the incidence of adverse events, each adverse event will be counted only once for a given patient within a specified SOC, preferred term. If the same adverse event occurs on multiple occasions for a patient, the occurrence with the highest severity and relationship to IMP will be reported. Changes in vital signs, hematology, and clinical chemistry parameters from baseline to the end of the trial will be examined. Treatment-emergent changes from normal values to abnormal values in key laboratory parameters will be identified. Effects on cognitive functions will be assessed summarizing changes from baseline in performance testing results with descriptive statistics.

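### Section 10.2 requires surgery planned before inclusion to go on the AE page although 10.2 and 10.6.1 say it is not an AE, so a few planned procedures could be tabulated as non-serious TEAEs

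*Combined protocol and SAP*

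**What the plan says.** Section 10.2 (Definition of Serious Adverse Events) deals with planned hospital care twice, in consecutive paragraphs.

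- The paragraph that defines hospitalization lists exceptions: hospitalizations for "administrative, surgical procedures planned before trial inclusion, trial-related and social purposes do not constitute AEs".
- The next paragraph begins: "Elective surgery or other scheduled hospitalization periods that were planned before the patient was included in this trial are not to be considered serious". It then adds: "However, the event must be reported on the AE page in the eCRF and commented upon".

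Section 10.6.1 (Procedures) says: "Diagnostic and therapeutic non-invasive and invasive procedures, such as surgery, should not be reported as AEs". It adds that "any procedures pre-planned before entering the trial (e.g. for pre-existing conditions) can be excluded", and it directs that the medical condition behind an unscheduled procedure be reported if that condition is itself an AE.

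Section 10.6 (Pre-existing conditions) keeps a condition present before the reporting period off the AE record unless it worsens or its episodes become more frequent.

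Section 12.4 (Safety Analysis) says: "AEs will be regarded as treatment-emergent adverse events (TEAEs) if they occur after first administration of" the study product. All TEAEs are then summarized by system organ class and preferred term.

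**The concern.** A site with a child whose elective operation was arranged before inclusion has two instructions. One paragraph of 10.2, together with 10.6.1, says the operation is not an AE. The following paragraph of 10.2 says it must go on the AE page. Both are live instructions to sites, and nothing says which prevails.

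Adverse event incidence is a main safety output of this small trial, which has no concurrent control arm to show what is background care. If some sites enter planned surgery and others do not, the tables mix two recording rules. Some entries could then describe care that was arranged before the drug was given. Section 12.4 states no step that would take them out again.

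**Working it through.** The plan gives no figure on this point to reproduce. The check is a comparison of texts, followed by the weight of one patient in an incidence table.

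**1. Do the instructions conflict?** For surgery planned before inclusion:

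- 10.2, hospitalization paragraph: not an AE.
- 10.2, next paragraph: not serious, but mandatory entry on the AE page.
- 10.6.1, first sentence: surgery is not to be reported as an AE.
- 10.6.1, last sentence: pre-planned procedures may be left out (permissive wording).
- 10.1.1: an AE is an untoward occurrence, which a planned operation is not.

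The second line contradicts the first and third. Suppose the word for what must be reported is read as the underlying condition rather than the operation. Section 10.6 then still excludes it unless it has worsened or its episodes have become more frequent, so that reading does not remove the conflict.

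**2. How far does the conflict reach?** The 10.2 exception names administrative, pre-planned surgical, trial-related and social hospitalizations. Section 10.6.1 speaks of procedures. A scheduled medical stay without surgery is in neither text. For such stays the AE-page sentence is odd, but it is not expressly contradicted.

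**3. When could an entry become a TEAE?**

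- Lower limit: non-serious events before the first dose go to medical history (10.8 and Table 1, footnote 18).
- Upper limit: AEs are reported until 3 weeks after the last dose (Table 1, footnote 18).
- With doses at the start of weeks 1 and 5, the window is 4 + 3 = 7 weeks. It is 3 weeks for a child who receives one cycle, and longer than 7 if cycle 2 is delayed under 6.1.4.

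**4. How much planned care falls in that window?** The documents give no count, but they point to little:

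- The recommended resection, irradiation and chemotherapy precede trial start (Appendix 2).
- The access device is placed before the first dose (Table 1, footnote 9).
- Additional anti-cancer therapy is prohibited from week -3 to week 9 (7.3.1).
- Admissions for the infusion are trial-related, and 10.2 already excepts them.

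**5. What is one entry worth?** Section 6.8 sets enrollment at 32 to 50. If all enrolled patients are treated, one affected patient adds 1/N to the incidence of the preferred term:

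- N = 32: 1/32 = 0.031, or 3.1 percentage points.
- N = 50: 1/50 = 0.020, or 2.0 percentage points.

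Several affected patients add up within one term only if they share that term.

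**The case against.** The strongest reply is that 12.4 applies the treatment-emergent rule to AEs, not to every row of an eCRF page. Planned surgery is not an AE under 10.1.1 or under 10.2's own exception. Section 10.2 also requires a comment on the entry, so it can be recognized, and 15.3 provides for manual medical checks. Section 12.1 leaves analysis detail and data handling to the SAP, so a filter may be set there. This stands to the extent that tabulation is a possibility and not a certainty. It does not repair the instruction: sites enter data from the protocol, and no filter is stated in the text reviewed.

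A second reply is that the harm is slight. Over-recording does not hide toxicity, and these entries are by definition not serious. A planned operation would ordinarily be judged unrelated, and TEAEs are also summarized by relationship. Headache, vomiting and fever are expected after infusion (10.7). In a child who already has one of these, a planned procedure would not change the count of patients with any TEAE. All of this stands and keeps the point minor.

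Three stronger readings are tempting, and the documents do not support them:

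- A reader might infer that the TEAE tables will be materially inflated because these children often have scheduled procedures. The documents give no such frequency, and the window and restrictions in the working suggest few.
- A reader might infer that every scheduled stay is caught in the contradiction. Stays without surgery are not named in the text that denies AE status.
- A reader might infer that a planned stay would be graded 3, because the Grade 3 text in 10.6.4 mentions hospitalization, and would so reach the secondary endpoint on severe events. The documents do not say how a planned stay would be graded.

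**Conclusion.** The contradiction is real and explicit for surgery planned before inclusion. Its consequence is a possibility that follows from 12.4 as written: such a procedure, if dated between the first dose and 3 weeks after the last, could be tabulated as a non-serious TEAE at one site and left unrecorded as an AE at another.

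The size per affected patient is 3.1 percentage points at 32 patients, falling to 2.0 at 50, on the incidence of one term. The number of such patients is not given and is probably small. Overall survival is unaffected, and so are SAE counts, because 10.2 states that these events are not serious.

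This rests on two assumptions: that sites follow the AE-page sentence as written, and that the SAP to which 12.1 defers contains no filter. It is a minor point, worth correcting because correction is cheap.

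**What to change.** Reconcile 10.2 with 10.6.1 in two steps.

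1. In 10.2, replace the AE-page sentence with an instruction to record pre-planned procedures and stays, including those after the first dose, in a named non-AE place in the eCRF. The medical and surgical history page, kept open for this purpose, would serve. An AE is entered only if the underlying condition worsens or a complication occurs.
2. In 12.4, add one line: pre-planned procedures already entered on the AE page are listed but excluded from the TEAE summaries.

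Deleting the sentence alone is not enough. Under 9.2.6 medical and surgical history is collected during screening, so a planned procedure after the first dose would have no stated place of record, and the explanation that supports its non-serious status would be lost.

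The cost is a small data-entry note for the eCRF and a review of existing AE-page entries. Worsening and complications would still be captured as AEs under 10.1.1, 10.6 and 10.6.1.

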10.3 Definition of non-serious AE

- A non-serious AE is any AE which does not fulfil the definition of an SAE.

10.4 Pre-defined AEs of Special Interest

The following AEs are selected as Adverse Events of Special Interest (AESIs) based on previously experience with ^{131}I -Omburtamab and should be reported within 24 hours to sponsor:

- Neurotoxicities Grade 3 and above
- Severe infections related to placement of cerebroventricular device
- Chemical meningitis

10.5 Adverse Event Recording

10.6 Pre-existing conditions

In this trial, a pre-existing condition (i.e. a disorder present before the AE reporting period started and noted on the medical history/physical examination form) should not be reported as an AE unless the condition worsens, or episodes increase in frequency during the AE reporting period.

10.6.1 Procedures

Diagnostic and therapeutic non-invasive and invasive procedures, such as surgery, should not be reported as AEs. A medical condition for which an unscheduled procedure was performed, should however be reported if it meets the definition of an AE. For example, an acute appendicitis should be reported as the AE and not the appendectomy. Additionally, any procedures pre-planned before entering the trial (e.g. for pre-existing conditions) can be excluded.

10.6.2 Overdose, medication errors and misuse

An overdose is defined as a patient receiving a dose of the IMP in excess of that specified in this protocol.

Medication errors and uses outside what is foreseen in the protocol, including misuse of the product may include:

- Administration of wrong drug
- Wrong route of administration, such as IV instead of intracerebroventricular
- Administration of an overdose with the intention to cause harm or misuse of trial product.
- Accidental administration of a lower or higher dose than intended. The administered dose must deviate from the intended dose to an extent where clinical consequences for the trial patient were likely to happen as judged by the investigator, although the clinical consequences did not necessarily occur.

Overdose and medication errors (exceeding $\pm 10\%$ as compared to protocol-specified dose) should be reported as protocol deviations to the sponsor. If an overdose, medication error, or misuse results in an AE, the AE must also be reported in the eCRF. If the event qualifies as serious it must be reported using the paper clinical AE report form in addition to the AE form in the eCRF.

10.6.2.1 ***Management of Overdose of ^{131}I -omburtamab***

Rescue medication to reverse the action of ^{131}I -omburtamab is not available. In case of overdose or other medication errors of ^{131}I -omburtamab patients, should receive supportive care according to local guidelines and potential side effects of ^{131}I -omburtamab should be treated systematically.

In the event of an overdose, the Investigator should:

- Contact Medical Monitor (for contact details, see the protocol front page)
- Closely monitor the patient for any AE and laboratory abnormalities
- In case of an AE, close medical supervision and monitoring should continue until the patient recovers.

10.6.3 **Pregnancy**

Any pregnancy that occurs during trial participation must be reported to sponsor within 24 hours of learning of its occurrence using the pregnancy form. Pregnant trial patients must be withdrawn from treatment immediately. The pregnancy must be followed up to determine outcome and status of mother and child. The child must be followed at least to the age of one month. Pregnancy complications and elective terminations for medical reasons must be reported as an AE or SAE. Spontaneous abortions must be reported as an SAE.

10.6.4 Severity

The Investigator will use the National Cancer Institute (NCI) CTCAE version 4.0 to describe the maximum severity of the AE, see below (US Department of Health and Human Services 2010). The grade assigned by the investigator should be the most severe, which occurred during the AE period:

- Grade 1: Mild; asymptomatic or mild symptoms; clinical or diagnostic observations only; intervention not indicated.
- Grade 2: Moderate; minimal, local or noninvasive intervention indicated; limiting age-appropriate instrumental Activities of Daily Living.
 - Instrumental Activities of Daily Living refer to preparing meals, shopping for groceries or clothes, using the telephone, managing money, etc.
- Grade 3: Severe or medically significant but not immediately life-threatening; hospitalization or prolongation of hospitalization indicated; disabling; limiting self-care Activities of Daily Living.
 - Self-care Activities of Daily Living refer to bathing, dressing and undressing, feeding self, using the toilet, taking medications, and not bedridden.
- Grade 4: Life-threatening consequences; urgent intervention indicated.
- Grade 5: Death related to AE.

Any change in severity grade represents a new AE subsequently, when an AE change severity, a new AE should be created with the changed severity.

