8.1.2 Secondary endpoints

1. CNS/LM PFS at 6 and 12 months will be estimated based on the time from first treatment dose to CNS/LM progression or death from any cause. Patients alive without CNS/LM progression at time of analysis, will be censored at last date of disease evaluation without evidence of progression.
2. OS at 12 months will be estimated based on the time from first treatment dose to death by any cause. Patients alive at time of analysis, will be censored at last date known to be alive.
3. ORR assessed as a combination of partial response and complete response as defined by the Response assessment in Neuro-Oncology (RANO) group criteria for brain metastasis (Lin et al, 2015) or leptomeningeal metastases as defined by EANO-ESMO criteria (Le Rhun et al, 2017). ORR will be assessed at 6 months after the first treatment dose of ^{131}I -omburtamab
4. ORR according to CSF cytology. Response is defined as a complete response when CSF converts from positive at baseline to negative after treatment with ^{131}I -omburtamab
5. Whole-body, organ, blood, and CSF radiation dosimetry.
6. Pharmacokinetic analysis of activity in blood and CSF including derivation of best-fit uptake and/or clearance parameters (half-times, maximum value) of time-activity concentration curves and of I-131 residence times (i.e., cumulated activity) concentrations (in $\mu\text{Ci}\cdot\text{h/g}$).
7. The frequency, type, and duration of treatment-emergent severe adverse events and serious adverse events, including clinically significant laboratory abnormalities. All adverse events will be graded according to Common Terminology Criteria for Adverse Events (CTCAE), version 4.0.
8. Performance assessment to monitor gross changes in neurological function is performed at week 26 and subsequently every 6 months during trial period.
9. The rate of ADA occurrence assessed three weeks after the first and second treatment dose of ^{131}I -omburtamab

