9.1.2.7 ***Anti-Drug-Antibody effects on PK and Safety.***

The ADA characterization will deliver occurrence rate of neutralizing antibodies in blood and cerebrospinal fluid (CSF) of exposed patients. Potential associated effects of any neutralizing ADA's on ^{131}I -omburtamab pharmacokinetics (PK) in blood and CSF and safety will be investigated.

9.1.2.7.1 *ADA effects on PK*

Radioactivity counts in blood and CSF will be measured at the following time points after treatment with ^{131}I -omburtamab:

- 1h after treatment
- 6h after treatment
- 24 after treatment
- 7 days after treatment.

The analysis will comprise an intra-patient comparison of PK parameters from the two dose administrations in patients with and without presence of neutralizing ADAs in blood or CSF.

9.1.2.7.2 *ADA effects on Safety*

The analysis will comprise a comparison of reported safety events after the second dose administration in patients with and without presence of neutralizing ADAs in blood or CSF.

9.2 **Other assessments**

9.2.1 **Hematology and clinical chemistry**

Hematology and clinical chemistry will be measured by a local laboratory during screening and in all following treatment cycles and will assess liver and kidney function (ALT, AST, alkaline phosphatase, albumin, bilirubin, BUN, glucose and creatinine), total protein and serum electrolytes (sodium, potassium, chloride and bicarbonate). Complete differential blood count, including eosinophils and platelets, will be performed during screening and in the cycles up to the follow-up at week 26. Thyroid stimulating hormone (TSH)/ free and total T4 to be assessed at screening, pre-dose week 1 and 4, pre-dose week 5 and 8, week 26 if applicable and weeks 52, 78, 104 130 and 156..

If abnormal serum glucose (CTCAE \geq Grade 2) is obtained, a fasting serum glucose is to be obtained at next patient visit. AE reporting of hyperglycemia will require fasting values to assess CTCAE grading.

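### Section 10.6.4 turns every grade change into a new adverse event, which conflicts with its own maximum-grade rule and with section 10.9, inflates event counts and can split one severe spell into several shorter records

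*Combined protocol and SAP*

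**What the plan says.** Section 10.6.4 gives two instructions on severity. Before the list of grades it says: "The grade assigned by the investigator should be the most severe, which occurred during the AE period". After the list it treats any change of grade as a separate event: "when an AE change severity, a new AE should be created with the changed severity".

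Four other places bear on how those records are used:

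- Section 8.1.2, secondary endpoint 7, covers "The frequency, type, and duration of treatment-emergent severe adverse events and serious adverse events, including clinically significant laboratory abnormalities".
- Section 12.4 plans event-level and patient-level summaries side by side: "The summaries will include number of events, number of patients, and percentage of patients reporting these events". For incidence it adds that "each adverse event will be counted only once for a given patient within a specified SOC, preferred term", with the highest-severity occurrence reported.
- Section 10.9 requires a follow-up report, not a new event, when an ongoing serious event changes in intensity.
- Section 10.6.6 refers to instructions accompanying the case report forms for changes in an ongoing event. Those instructions are not in the supplied documents. Its list of outcomes has no term for a record closed only because the grade changed.

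**The concern.** The two sentences of 10.6.4 describe different units of observation. Under the first, a record is an episode and its grade is the peak. Under the second, a record is a period at constant grade. Sites that follow different sentences will return data that mean different things, and the planned event counts and durations will depend on which sentence was followed.

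Grade changes are foreseeable here. Section 10.7 lists neutropenia and myelosuppression as expected, Table 1 schedules hematology in every treatment week, and section 11.1 requires Grade 4 laboratory values to be retested within 24 hours. Two outputs are exposed: the number-of-events column in the safety tables, and the duration component of secondary endpoint 7. With an enrollment of 32 to 50 patients (section 6.8), a few split episodes could visibly alter either one.

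**Working it through.** The documents give no adverse-event data and no figure on this point, so there is nothing to reproduce. The check has two parts: the text, then counts on assumed grade courses.

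**Text.**

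1. If every grade change opens a new record, each record holds exactly one grade. Its maximum is that grade, so the worst-grade instruction never operates.
2. Section 10.9 keeps a serious event as one event when its intensity changes. Section 10.6.4 makes no exception for serious events. The two conflict for serious events and for events of special interest, which section 10.8 says are to be reported as serious.
3. The once-per-patient rule in 12.4 governs incidence. It cannot also govern the number-of-events column: within a preferred term, that column would then always equal the number of patients. Event counts are therefore taken from records, and no supplied text says how consecutive records are joined.

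**Counts.** Assumptions: severe means Grade 3 or higher, and the grade courses and phase lengths are invented for illustration. Formulas:

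- records under the split rule = grade changes + 1
- mean record length = total days / records
- severe records = number of phases at Grade 3 or higher

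Under a one-episode rule every course below counts as one event.

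| Grade course | Phase lengths (days) | Records, split rule | Mean record (days) | Severe records (mean days) | Continuous severe spell (days) | Whole episode (days) |
|---|---|---|---|---|---|---|
| 3 | 14 | 0 + 1 = 1 | 14 | 1 (14) | 14 | 14 |
| 2-3-2 | 4, 6, 4 | 2 + 1 = 3 | 14/3 = 4.67 | 1 (6) | 6 | 14 |
| 3-4-3 | 5, 4, 5 | 2 + 1 = 3 | 14/3 = 4.67 | 3 (14/3 = 4.67) | 14 | 14 |
| 1-2-3-4-3-2-1 | 3 each | 6 + 1 = 7 | 21/7 = 3.0 | 3 (9/3 = 3.0) | 9 | 21 |
| 3-4-3 | 5, 7, 9 | 2 + 1 = 3 | 21/3 = 7 | 3 (21/3 = 7) | 5 + 7 + 9 = 21 | 21 |

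Three things follow. The event count rises by one per recorded grade change. The severe part is broken up only when the grade moves between 3 and 4: the 2-3-2 course keeps a single severe record. In every row the patient count is one and the worst grade is the same under either rule.

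**The case against.** The best defence has four parts.

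**The linking rule may exist elsewhere.** The case report form instructions cited in 10.6.6, or the detailed analysis plan promised in 12.1, may join the records. That is possible, and it limits the claim to the supplied text. It would not remove the contradiction inside 10.6.4 or the mismatch with 10.9.

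**The main safety outputs are protected.** This stands. A reader might infer that adverse-event incidence is overstated. It is not, because 12.4 counts each patient once per preferred term at the highest severity. The frequency in endpoint 7 can also be read as that incidence, in which case only the separate event count and the durations are affected. For serious events the follow-up route in 10.9 may keep the safety report as one event, although the eCRF record could still be split.

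**Worked examples can overstate the effect.** This also stands. A cytopenia passing through Grade 2, 3, 4, 3 and 2 need not produce five events, because section 10.1.1 makes a laboratory abnormality an adverse event only if it is clinically significant and needs active management. Section 10.9 ends follow-up of non-serious events 3 weeks (21 days) after the last dose, so after the final dose a 21-day course fits only if it begins at dosing. No median or other duration summary is specified in 12.4.

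**Grade-level records are useful.** Agreed. They keep dates that a single maximum-grade record would lose. The defect is in calling each one a separate event with no episode rule.

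A further inference is tempting: that an event from cycle 1 which merely improves after the second dose would count as new toxicity in the anti-drug-antibody analysis. Section 9.1.2.7 plans only a "comparison of reported safety events after the second dose administration" between patients with and without neutralizing antibodies. It sets no event-count measure and no onset rule, and the recording rule is the same in both groups. An effect is possible but neither its existence nor its direction is shown.

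**Conclusion.** The point holds in a limited form. Section 10.6.4 contains two rules that cannot both act on one record, and the second also conflicts with 10.9. Followed as written, the split rule raises the planned number of events by one for each recorded grade change. It also shortens recorded durations and, where a severe spell moves between Grades 3 and 4, divides that spell into several severe records. In the assumed courses one episode yields between one and seven records, and severe spells of 9 to 21 days that include such a move appear as three records averaging 3.0 to 7 days. The real size cannot be estimated without adverse-event data.

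The conclusion assumes that severe means Grade 3 or higher and that no unsupplied document joins the records. Total days at each grade remain recoverable from the dates, so no information is permanently lost where sites follow the split rule. Safety is summarized descriptively in a single-arm trial with survival as the primary endpoint. Priority is minor to moderate.

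**What to change.** 1. Reword 10.6.4 so that a grade change is a dated grade entry linked to the same adverse event, not a new one. The maximum-grade instruction then has a clear meaning. Align the wording with 10.9 and with the case report form instructions.
2. State in 12.4 and the analysis plan that contiguous records of the same preferred term in a patient are collapsed into one episode before events are counted. Grade the episode at its maximum.
3. Define episode duration as first onset to final resolution, and report time at Grade 3 or higher separately. Show an episode still open when follow-up ends as ongoing.

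The cost is a wording change and one programming rule applied to terms, grades and dates already collected. Event counts will be lower and severe durations longer than under the present text. Patient-level incidence and worst grade will not change.
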